 - Some patients on IrCs experience mild clumsiness, tremor, nausea or abdominal griping during the three days of Cs treatment. Reassurance and general symptomatic treatments are normally sufficient; but if severely affected, reduce the Cs dose to 2 mg/kg t.d.s. for the remainder of the cycle and for all subsequent cycles.

- Some patients find the smell or taste of Cs foul. We recommend:
 - try switching from gelatin capsules to liquid or vice versa
 - “pop” the capsule blister-packs out-doors to avoid the smell
 - liquid may be mixed with orange juice to disguise the taste
- If a patient on IrCs is unable to tolerate Cs even with the above measures, they should cross over to standard Ir. However please see note in 6.5 regarding irinotecan dosing.

6.5 Cross-over

- Crossover involving ciclosporin:
 - Cross-over from **IrCs** to **Ir** should be avoided if possible, however if a patient cannot tolerate Cs this may be necessary. Please inform the CTRU.
 - the half-life of Cs is around 6 hours in most patients but may be as long as 20 hours. Therefore at least 1 week wash-out time must be allowed after the patient took their last Cs dose, before they receive standard-dose Ir.
 - Cross-over from **Ir** or **IrPan** to **IrCs** is not permitted
- Crossover involving Panitumumab:
 - Cross-over from **IrPan** to **Ir** should be avoided if possible, however if a patient cannot tolerate Pan this may be necessary. Please inform the CTRU.
 - Cross-over from **Ir** or **IrCs** to **IrPan** is not permitted.

6.6 Concomitant therapy

- Drugs which are potent inhibitors of CYP3A4 should be avoided, as they may affect irinotecan and/or ciclosporin metabolism. These include:
 - antifungals: ketoconazole; fluconazole; itraconazole
 - antibiotics: erythromycin; clarithromycin; norfloxacin
 - cardiac drugs: diltiazem; verapamil; amiodarone
 - antidepressants: fluvoxamine
- Many other drugs are substrates, inducers or mild inhibitors of CYP3A4. Interactions with irinotecan and ciclosporin are possible, but not known to be of major clinical significance. Use caution.
- Grapefruit juice contains potent CYP3A4 inhibitors and should be avoided for 3 days before and after each chemotherapy treatment
- Metoclopramide may increase Cs levels therefore we do not recommend metoclopramide as an antiemetic for patients randomised to IrCs. Please use domperidone as an alternative.

6.7 Radiotherapy

Please avoid treating patients with radiotherapy during the initial 12 weeks of treatment; however if palliative radiotherapy is required for pain control this may be given. In this case radiotherapy should not be given during the 2 days before or the 5 after a dose of irinotecan. Full dose radical radiotherapy should not be used concurrently with PICCOLO treatment. Great care should be taken if radiotherapy is to the small or large bowel.

6.8 Pharmacokinetics Sub-study (see Appendix 4)

- In 20 consenting patients recruited to the IrCs arm in 2-4 centres with pharmacokinetics (PK) expertise, the plasma AUC of Ir and its metabolites will be compared during Ir and IrCs treatments during two consecutive cycles as follows:
 - For patients allocated **IrCs**, and participating in the PK Sub-study, two consecutive cycles during the first 4 cycles of therapy (i.e. cycles 1 & 2, cycles 2 & 3 or cycles 3 & 4) will be nominated as PK Sub-study cycles
 - For these two cycles the patient will receive, in random order, one cycle of IrCs and one cycle of standard Ir
 - PK blood sampling will be performed during the nominated cycles, as per Appendix 4

6.9 Drug Supply

Panitumumab will be supplied, packaged and labelled as per the requirements of the Medicines for Human Use (Clinical Trials) Regulations 2004.

Off-the-shelf supplies of irinotecan and ciclosporin will be used and labels will be provided for use at the time of dispensing.

6.10 Withdrawal of Treatment

In line with usual clinical care, cessation or alteration of regimens at any time will be at the discretion of attending clinicians or the patients themselves. All patients withdrawn from treatment or prescribed an alternative treatment will still attend for follow-up assessments unless unwilling to do so and Case Report Forms will continue to be completed.

If a patient explicitly states they do not wish to contribute further data to the study the CTRU should be informed in writing.

7. ASSESSMENTS/DATA COLLECTION

The trial consists of an initial 12-week treatment period, with further treatment until treatment failure (progression or toxicity). All patients will be followed up every 12 weeks until one year post-randomisation or death.

Trial data will be recorded by hospital research staff on the Case Report Forms (CRFs) and submitted to the CTRU at the University of Leeds. At the end of the trial, data will be securely archived at the CTRU and participating centres for a minimum of 15 years. Following

authorisation from the Sponsor, arrangements for confidential destruction will then be made. If a patient withdraws consent for their data to be used, it will be confidentially destroyed. It is the responsibility of each centre to retain copies of all completed CRFs and to maintain their file of essential trial documentation on site or at their designated archive facility.

7.1 Schedule of events

	Prior to registration	Prior to randomisation	Baseline (up to 4 weeks prior to treatment)	Day 1 of each cycle	12-Week Reassessment	Follow-up every subsequent 12 weeks, until one year post-randomisation
Informed consent for K-RAS test	X					
Informed consent to participate in the main trial		X				
Patient details (initials, date of birth, sex, hospital number)		X				
Serum or urine HCG ^a		X ^b				
Medical history ^c		X				
Physical examination ^d		X		X ^e		
Laboratory tests ^f		X		X ^e		
Concomitant diseases & medication		X		Monitor throughout study		
Quality of Life questionnaires		X ^g				
NCI-CTC[V3] grades				X	X	X
CT scan			X		X	X ^h
Adverse events				Monitor throughout study		
Survival/recurrence of disease				Monitor throughout study		

^a If the patient is female and of child bearing potential

^b Taken up to 72 hours prior to randomisation

^c Including prior treatment with irinotecan, an anti-EGFR targeted therapy, oxaliplatin and bevacizumab

^d Including height, weight, body surface area and WHO performance status

^e Day 1 of each cycle or up to 5 days prior

^f Including a combination of FBC, LFTs, U&Es, magnesium & calcium

^g Further questionnaires at 12 and 24 weeks will be posted to the patients by the CTRU

^h Or sooner if clinically indicated

7.2 Pre-randomisation Assessments

Post written informed consent and prior to randomisation, the following investigations and assessments will be carried out:

- Medical history including prior treatment with 5FU, capecitabine, oxaliplatin, bevacizumab or an anti-EGFR targeted therapy,, best response to previous drug therapy and dose delays/reductions for toxicity during previous drug therapy. Details of concomitant disease and medication will also be collected.
- Physical examination including height, weight, body surface area and WHO performance status
- Laboratory tests including FBC, LFTs, U&Es
- If the patient is female and of childbearing potential, a negative serum or urine HCG pregnancy test within 72 hours of trial entry
- Baseline Quality of Life questionnaires (for details please refer to section 7.8)

In addition the following data will be collected:

- Patient's GP name and address
- Patient's personal details and demographics

7.3 Baseline Assessments

The baseline CT scan must be carried out no more than 4 weeks prior to the start of trial treatment. Please note that trial treatment must start no more than 2 weeks post-randomisation. See section 5.3 for details.

7.4 Translational Research

N.B. This section applies to patients who have consented to participate in the associated translational research (optional points 11 and 12 on the PICCOLO Patient Information Sheet and Consent Form document).

A 10ml blood sample (in at EDTA tube) and a 20ml urine sample (in a plain collection tube) will be collected prior to the start of any trial treatment. The samples should be labelled with the patients' trial number only. Please send the blood and urine samples to the appropriate lab using the pre-paid, addressed safe boxes provided by the CTRU.

7.5 Treatment Assessments

Patients will be assessed clinically for symptoms and toxicity at the start of each drug therapy cycle i.e. 3-weekly. The CRF completed at these visits will include specific questions about the expected side-effects of the study drugs (using NCI-CTC version 3), plus any additional side effects, during the preceding cycle. Serious adverse events will be reported according to the Medicines for Human Use (Clinical Trials) Regulations 2004 (see section 8). On Day 1 of treatment (day of irinotecan infusion) the following investigations and assessments will be carried out:

- Height, weight, body surface area and WHO performance status (may be assessed up to 5 days prior to Day 1)
- Laboratory tests including FBC, LFTs, U&Es, magnesium and calcium (may be assessed up to 5 days prior to Day 1)
- Toxicity relating to the previous cycle assessed by NCI-CTC[V3] grades

In addition the following data will be collected:

- Cycle details including dose given, dose alteration/delay and reason

N.B. When a patient permanently stops trial treatment please fax a copy of the completed Treatment Stop Fax (section 7 of the Investigator Site File) to the CTRU.

7.6 12-Week Reassessment

At 12 weeks post-randomisation the following investigations and assessments will be carried out:

- Reassessment CT scan and response by RECIST criteria
- Toxicity assessed by NCI-CTC[V3] grades

In addition the following data will be collected:

- Clinical evidence of disease progression or not
- Treatment plan (i.e. continue or stop treatment)
- Details of any non-trial anti-cancer treatment received since randomisation
- Quality of Life questionnaires (for details please refer to section 7.9)

7.7 Progress and Follow-up Assessment

Follow-up data will be collected at 24 weeks post-randomisation and 12-weekly thereafter for all patients until 48 weeks post-randomisation, or until 6 weeks after the last PICCOLO treatment, whichever is later. The information required at these time-points includes late toxicity (adverse events occurring up to six weeks after the last dose of irinotecan), subsequent therapy and death.

The following investigations and assessments will be carried out:

- CT scan and response by RECIST criteria (if progression has not previously occurred).
- Toxicity assessed by NCI-CTC[V3] grades (up to 6 weeks after last study treatment dose)

In addition the following data will be collected:

- Patient status
- Summary of trial treatment since last assessment
- Details of any non-trial anti-cancer treatment received since last assessment
- Clinical evidence of disease progression or not
- Treatment plan
- Quality of Life questionnaires at 24 weeks post-randomisation (for details refer to section 7.9)

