7.9 Deaths

Death must be recorded on the Death Form. The date and cause of death will be collected. Death forms must be returned to CTRU within 7 days of the death being notified to the site team.

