7.11 Definition of End of Trial

The end of the trial is defined as the date of the last visit of the last patient undergoing the protocol based drug therapy. Follow-up will continue for one year after the last patient is randomised.

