Although not primarily designed to detect superior efficacy for IrCs compared with Ir, this is a possible consequence of reduced toxicity if it leads to improved treatment duration. The proposed sample size will provide 80% power to detect an increase in median PFS of 1.1 months, or an increase in OS of 2.9 months with Cs, using a 2-sided log-rank test at the 5% significance level.

Ir vs IrPan comparison (patients with wild-type *K-RAS* status not previously receiving an anti-EGFR targeted therapy)

For the +/- panitumumab comparison, a superiority design is proposed, based upon overall survival (OS). Previous literature has found median OS for patients taking Ir to be between 9.2 and 10.8 months, mostly in patients pre-treated with only FU/LV.^{38,40} Since many PICCOLO patients will have received FU/LV and oxaliplatin, we have assumed a slightly shorter median OS of 9 months in the control arm.

Since this comparison considers patients with wild-type *K-RAS* status only, for whom we expect the benefit of the addition of panitumumab to irinotecan to be increased, the study is now powered to detect a reduction in hazard rate of 30% with the addition of panitumumab, compared to no panitumumab. With 80% power and a significance level of 5%, 466 patients (246 deaths) are required to test for this degree of superiority using a 2-sided log-rank test, assuming patients are followed for a fixed length of time and that the hazard ratio is constant. 480 patients (240 per arm) will therefore be recruited to allow for loss to follow-up.

Previous anti-EGFR targeted therapy use

We expect that approximately 15% of patients recruited to PICCOLO will have previously been treated with an anti-EGFR targeted therapy. It is possible that there will be cross-resistance between anti-EGFR targeted therapies and other EGFR agents including panitumumab, and it is therefore important that the Ir vs. IrPan comparison compares only patients who have not

previously received anti-EGFR targeted therapies. This comparison will therefore include all patients who have not previously received an anti-EGFR targeted therapy who have been randomised to receive either Ir or IrPan (and who have wild-type *K-RAS* status).

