Since we are assessing inferiority and superiority of IrCs at the interim analysis, and non-inferiority of IrCs in the final analysis, we have not adjusted the α -levels of the CIs at the final analysis for this comparison. Different α -levels have been incorporated to reflect the relative importance of the interim analysis for superiority and inferiority claims.

Using the 0.1% significance level for the Ir vs. IrPan comparisons at the interim analysis controls the type I error using the methods of Haybittle-Peto⁴⁵. By using such a conservative alpha at the interim analysis this allows us to maintain an overall critical value of 5% at the final analysis, for this comparison.⁴⁶

There will be no formal statistical analysis of the exploratory endpoints for those patients who have previously received anti-EGFR targeted therapies, or have mutant or unknown *K-RAS* status, for the Ir vs. IrPan comparison.

If the DMEC recommends continuation of the trial they will assess cross-over rates specifically from IrCs, with a recommendation of whether it is necessary to increase the sample size to allow for higher cross-over. No other statistical analyses are planned until after the trial is closed to accrual. The first main report/publication of the trial will be prepared when, for the Ir/IrCs comparison every patient has reached 12 weeks follow-up, and for the \pm panitumumab comparison when the required event rate of 246 deaths has occurred between the Ir and IrPan arms (patients with wild-type *K-RAS* status not previously receiving anti-EGFR targeted therapies) and when median follow up of at least one year has been reached. The database will be locked prior to the each main analysis. Longer-term endpoints for the Ir/IrCs comparison will be analysed when the required event rate of 273 PFS events across the Ir and IrCs arms, and median follow-up of one-year, has been reached.

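### The protocol sets conflicting limits on survival follow-up, and two of its three rules leave little or no room to meet the overall-survival analysis trigger

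*Protocol*

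**What the plan says.** The protocol states how long patients are followed in three ways:

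- **Section 7.7:** data are collected at 24 weeks and "12-weekly thereafter for all patients until 48 weeks post-randomisation, or until 6 weeks after the last PICCOLO treatment, whichever is later". Death and patient status are among the items listed, so the limit is not confined to scans and toxicity.
- **Sections 7 and 7.1:** "All patients will be followed up every 12 weeks until one year post-randomisation or death", and the schedule's last column is headed "Follow-up every subsequent 12 weeks, until one year post-randomisation".
- **Section 7.11:** "Follow-up will continue for one year after the last patient is randomised". The survival row of the section 7.1 table, which has no stated end, reads "Monitor throughout study".

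Two other places bear on vital status. Section 7.9 says "Death forms must be returned to CTRU within 7 days of the death being notified to the site team", with no limit counted from randomisation. Section 12 censors OS at the date last known alive, with no cap at 48 weeks or one year.

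Section 12.1 ties the Ir vs IrPan report to 246 deaths and adds "when median follow up of at least one year has been reached". Section 11.1 sizes the comparison at 466 patients and 246 deaths, "assuming patients are followed for a fixed length of time", without giving that length. The recruitment target is 480.

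**The concern.** The OS report is event-driven and also has a follow-up condition, so it depends on how long survival is collected. A per-patient stop fixes the maximum number of deaths available. If that maximum falls short of 246, waiting longer adds nothing. A stop shorter than one year also conflicts directly with the one-year median.

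The conflict also affects data quality. Sites that follow section 7.7 and sites that follow section 7.11 would supply different survival data. If late deaths arrive by Death Form while survivors are last contacted at week 48, censoring at last known alive biases the survival curves downward.

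**Working it through.** **Inputs from the protocol.** Control median OS 9 months, hazard ratio (HR) 0.70, 80% power, two-sided 5%, 466 patients and 246 deaths, 480 recruited 1:1 (section 11.1). About 143 patients entered under Version 1 and about 337 enter later (section 3). Recruitment lasts three years with 18 months remaining (section 11.2). Median progression-free survival (PFS) on irinotecan is 4.2 months (section 11.1).

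**Assumptions added here.** Exponential survival; uniform accrual within months 0–18 (143 patients) and 18–36 (337 patients); no loss to follow-up unless stated.

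**1. The protocol's figure.** By Schoenfeld's formula, deaths = 4(1.96 + 0.842)² / (ln 0.7)² = 246.8, and 246 deaths give 79.9% power. The stated 246 is reproduced. With S(t) = 0.5^(t/9), the probability of death by t, averaged over the arms, is q(t) = 1 − [S(t) + S(t)^0.7]/2. Setting q(t) = 246/466 = 0.528 gives t = 11.6 months. The sizing therefore fits follow-up of about one year.

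**2. Per-patient caps, 480 patients.**

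| Cap | q | Expected deaths | Chance of at least 246 |
|---|---|---|---|
| 48 weeks (11.04 months) | 1 − (0.427 + 0.552)/2 = 0.511 | 245 | 48% |
| 12 months | 1 − (0.397 + 0.524)/2 = 0.540 | 259 | 89% |

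With assumed losses of 3%, 5% or 10% per year, the 48-week figure becomes 242, 240 or 235. The 12-month figure becomes 256, 253 or 248.

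**3. Sensitivity to the control median.** Section 11.1 cites 9.2 to 10.8 months and assumes 9. At 10 months with HR 0.70, a 12-month cap gives about 241 deaths (36% chance of 246). At 10.8 months it gives about 229 (6%).

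**4. The median follow-up condition.** Under section 7.7, reaching one year needs treatment at or after week 46 (52 − 6). Take exponential PFS with median 4.2 months, apply HR 0.70 to IrPan PFS as well, and assume every progression-free patient is still on treatment. The shares at week 46 (10.58 months) are then 17% on Ir and 29% on IrPan. As a share of those alive at week 48, the pooled figure is (0.174 + 0.295)/(0.427 + 0.552) = 48%. That is an upper bound, because some patients stop for toxicity, and it is still under half. The median stays at 48 weeks, or 0.92 year. Under a 12-month cap the median can at best equal one year.

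**5. Follow-up to one year after the last randomisation (month 48).** The average of S over follow-up from u to v is [S(u) − S(v)] / [λ(v − u)], with λ = 0.0770 for Ir and 0.0539 for IrPan.

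- First 143 (30–48 months of follow-up): surviving 0.054 and 0.127, mean 0.090; deaths 143 × 0.910 = 130.
- Later 337 (12–30 months of follow-up): surviving 0.215 and 0.335, mean 0.275; deaths 337 × 0.725 = 244.
- Total: 374. Power = Φ(√(374/4) × 0.357 − 1.96) = 93%.

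With no cap, 246 deaths are reached near month 35. At accrual close (month 36) there are about 254 deaths and a median potential follow-up of 12.8 months, so both conditions are met. Under a one-year cap, 246 deaths are reached near month 42.

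**6. Deaths beyond a cap.** 374 − 259 = 115 and 374 − 245 = 129. The Version 1 patients supply 130 − 77 = 53 or 130 − 73 = 57 of these.

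**7. Mixed collection.** In an extreme simulated case, every death to month 48 is reported but no survivor is contacted after week 48. The Ir Kaplan-Meier estimate at 18 months is then 16%, against a true 25%.

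**The case against.** A reader might infer that the trigger cannot be met as written. The documents do not support that. The survival row in section 7.1, the Death Form rule in 7.9, the statement in 7.11 and the censoring rule in section 12 all fit open-ended survival follow-up, under which both conditions are met near the close of accrual. A one-year cap also reaches 246 on the stated assumptions. Even a strict 48-week stop leaves about an even chance on deaths; its real obstacle is the one-year median. The gap between 48 weeks and one year may simply reflect a 12-weekly visit grid. All of this stands.

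A reader might also infer that over 100 deaths from early recruits are thrown away. The count holds only if a cap applies. The deaths come from everyone with more than a year of potential follow-up, and fewer than half come from the Version 1 patients. Nor are they a shortfall: the plan chose 80% power at 246 deaths.

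The supporting passages still do not settle the matter. Section 7.11 is compatible with a one-year cap, since the last patient simply completes a year. The survival row has no defined end and sits beside a one-year column. Section 7.9 acts only once a death is notified and does not require checks on living patients. Section 7.7 names death and patient status within its limit.

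**Conclusion.** The protocol contradicts itself on how long its primary endpoint is collected, and the consequences differ by reading. A literal 48-week stop very likely fails the one-year median condition and leaves about an even chance of 246 deaths. A one-year cap works at a 9-month control median but has no margin on median follow-up, and falls to about 241 deaths at a 10-month median. Follow-up to one year after the last randomisation satisfies the trigger, with about 374 deaths by month 48 and about 93% power if all are analysed.

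These figures rest on exponential survival, HR 0.70 and uniform accrual within the 143/337 split. Uniform accrual over all 36 months would give about 392 deaths by month 48. The contradiction itself depends on no assumption.

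**What to change.** State one rule and align sections 7, 7.1, 7.7, 7.11 and 12.1 with it. Vital status (date of death, or date last known alive) is actively collected for every randomised patient to a common cut-off no earlier than the OS analysis and one year after the last randomisation. All deaths to that date are analysed, with 246 as the minimum. Visits, scans and toxicity collection keep their present schedule.

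The cost is protocol wording plus periodic status checks on living patients. No visits, scans or patients are added.
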